4.2.2. Exclusion Criteria

Subjects who meet any of the following exclusion criteria are not eligible for study participation:

- 1) Known histological transformation from iNHL or CLL to an aggressive form of NHL (ie, Richter transformation) if the CLL patient has not had ibrutinib or idelalisib as their immediately prior therapy. CLL patients who were treated with a BCR inhibitor as the most recent therapy and who experience a transformation of their tumor, will not be excluded. Subjects who have a history of iNHL or CLL with a subsequent confirmation high grade histology will be considered transformed for purpose of this study. *Note: Biopsy documentation of the absence or presence of transformation is not required*
- 2) Known active central nervous system or leptomeningeal lymphoma. *Note: Central nervous system imaging is only required in subjects with suspected lymphomatous involvement based on symptoms or signs*
- 3) Presence of known intermediate- or high-grade myelodysplastic syndrome (ie, subjects are excluded who have ≥ 5 bone marrow blasts; karyotypic abnormalities other than normal, Y deletion, 5q deletion, or 20q deletion; or ≥ 2 lineages of cytopenias) {Greenberg 1997}
- 4) Because they are likely to interfere with GS-9973 absorption, current therapy with agents that reduce gastric acidity, including but not limited to proton pump inhibitors
- 5) History of any prior lymphoid malignancy other than registration histology except for CLL subjects with prior BCR therapy
 - a) Subjects with diagnoses other than CLL who were previously treated with a BCR inhibitor are excluded from this study.

- 6) History of non-lymphoid malignancy except for the following: adequately treated local basal cell or squamous cell carcinoma of the skin, cervical carcinoma in situ, superficial bladder cancer, asymptomatic prostate cancer without known metastatic disease and with no requirement for therapy or requiring only hormonal therapy and with normal prostate-specific antigen for ≥ 1 year prior to start of study therapy, other adequately treated Stage 1 or 2 cancer currently in complete remission, or any other cancer that has been in complete remission for ≥ 5 years
- 7) Evidence of ongoing systemic bacterial, fungal, or viral infection at the time of start of study drug. **Note: Subjects with localized fungal infections of skin or nails are eligible.**
- 8) Ongoing, drug-induced liver injury, chronic active Hepatitis C Virus (HCV), chronic active Hepatitis B Virus (HBV), alcoholic liver disease, non-alcoholic steatohepatitis, primary biliary cirrhosis, ongoing extrahepatic obstruction caused by cholelithiasis, cirrhosis of the liver, or portal hypertension
- 9) Ongoing (within the past 6 weeks) hepatic encephalopathy
- 10) Ongoing drug-induced pneumonitis
- 11) Ongoing inflammatory bowel disease
- 12) Ongoing alcohol or drug addiction as determined by investigator
- 13) Pregnancy or breastfeeding
- 14) History of prior allogeneic bone marrow progenitor cell or solid organ transplantation
- 15) Ongoing immunosuppressive therapy, including systemic corticosteroids for treatment of lymphoid malignancy. Concurrent use of methotrexate for rheumatologic conditions is permitted. Note: Subjects may use topical, enteric, or inhaled corticosteroids as therapy for comorbid conditions and systemic steroids for autoimmune anemia and/or thrombocytopenia. Ongoing use of low-dose systemic corticosteroids (≤ 5 mg/day of methylprednisolone or equivalent) for rheumatologic conditions is permitted. During study participation, subjects may receive systemic or other corticosteroids needed for treatment-emergent comorbid conditions. See next entry for exception related to steroids.
- 16) Concurrent participation in an investigational drug trial with therapeutic intent defined as prior study therapy within 21 days prior to study drug. Exception: the cohorts with relapsed CLL following BCR pathway inhibitors whom in the opinion of the investigators cannot have a 21 day washout period. ≥ 5 half lives washout period will be allowed, along with up to 20 mg of prednisone at the start of the trial, for control of disease related symptoms, with planned taper over 2 weeks
- 17) Any other prior or ongoing condition that, in the opinion of the investigator, could adversely affect the safety of the subject or impair the assessment of study results

5. INVESTIGATIONAL MEDICINAL PRODUCTS

5.1. Enrollment

It is the responsibility of the Investigator to ensure that the subjects are eligible for the study prior to enrollment. Once eligibility is confirmed subjects will be assigned a unique subject number. In this open-label study all subjects will receive up to 800 mg GS-9973 BID or one of 3 doses (100 mg, 200 mg or 400 mg) of GS-9973 SDD BID under fasted conditions (as defined in Section 5.5.10). As of protocol amendment 8, subjects receiving GS-9973 MM formulation will be transitioned to the GS-9973 SDD formulation (Section 5.3.5). All baseline tests and procedures must be completed prior to the administration of the first dose of study drug on Day 1. Once a subject number is assigned to a subject, it will not be reassigned to another subject.

5.2. Description and Handling of GS-9973 and GS-9973 SDD

5.2.1. Formulation

GS-9973 tablet is available as 200 mg strength tablets. The tablets contain commonly used excipients including lactose monohydrate, microcrystalline cellulose, crospovidone, povidone, sodium lauryl sulfate, silicon dioxide, magnesium stearate, polyethylene glycol, polyvinyl alcohol, talc, titanium dioxide, and FD&C blue #2 aluminum lake. The 200 mg GS-9973 tablets are capsule-shaped, plain-faced, film-coated blue tablets.

GS-9973 SDD (ENTO) tablets, 100 mg and 200 mg strength, are available as blue, capsule-shaped film-coated tablets that are plain-faced. In addition to the active ingredient, ENTO tablets contain the following inactive ingredients: methanesulfonic acid, hydroxypropyl methylcellulose (hypromellose),mannitol, microcrystalline cellulose, crospovidone, poloxamer 188, silicon dioxide, magnesium stearate, polyethylene glycol, polyvinyl alcohol, talc, titanium dioxide, and FD&C blue #2 aluminum lake.

GS-9973 SDD (ENTO) tablets, 200 mg strength, are also available as beige, capsule-shaped film-coated tablets debossed with “GSI” on one side and “9973” on the other side. In addition to the active ingredient, ENTO tablets contain the following inactive ingredients: methanesulfonic acid, hydroxypropyl methylcellulose (hypromellose),mannitol, microcrystalline cellulose, crospovidone, poloxamer 188, silicon dioxide, magnesium stearate, polyethylene glycol, polyvinyl alcohol, talc, titanium dioxide, ferrosferric oxide/black iron oxide, iron oxide red, and iron oxide yellow.

5.2.2. Source

GS-9973 and GS-9973 SDD will be supplied free of charge by Gilead Sciences. Any questions or concerns regarding study drug supply should be referred to the Gilead Sciences clinical project manager.

5.2.3. Packaging and Labeling

Sixty (60) GS-9973/GS-9973 SDD tablets are packaged in white, high-density polyethylene bottles with silica gel desiccant, and polyester packing material. Each bottle is capped with a child-resistant polypropylene screw cap fitted with an induction-sealed, aluminum-faced liner.

All study drug labels will meet all applicable requirements of the protocol and the regulatory authorities.

5.2.4. Storage and Handling

GS-9973 tablets should be stored at a controlled room temperature of 25 °C (77 °F); excursions are permitted from 15 °C to 30 °C (59 °F to 86 °F).

GS-9973 SDD tablets should be stored at a controlled room temperature of 25 °C (77 °F); excursions are permitted from 15 °C to 30 °C (59 °F to 86 °F).

Measures that minimize drug contact with the body should always be considered during handling, preparation, and disposal procedures. Any unused study drug should be disposed of in accordance with local requirements.

5.2.5. Study Drug Accountability

The investigator or designee (eg, pharmacist) is responsible for ensuring adequate accountability of all used and unused study drug bottles during the study. This includes acknowledgement of receipt of each shipment of study drug (quantity and condition) and tracking of bottles assigned/utilized for subject dosing. All unused study drug bottles must be returned to the site by the subjects.

Investigational Drug Accountability records will be provided to each study site to:

- Record the date of receipt and quantity of study drug.
- Record the date of dispensation, subject identifier, and study drug bottle number(s) dispensed.
- Record the date of return and quantity of used and unused study drug bottle(s).

Dispensing records will include the initials of the person dispensing the study drug or supplies.

5.3. Treatment Plan

5.3.1. Premedication

No specific premedications or supporting medications are required in conjunction with GS-9973/GS-9973 SDD administration, although institution of antibiotic prophylaxis for *Pneumocystis (carinii) jiroveci* may be considered in all subjects (see Section 5.5.3).

5.3.2. Administration Instructions

GS-9973/GS-9973 SDD should be taken under fasted conditions (as defined in Section [5.5.10](#)). Subjects should be instructed not to bite or chew the tablets. In case of breakage of the tablets in the oral cavity, additional water should be taken as a rinse.

5.3.3. Dosing Schedule

GS-9973/GS-9973 SDD should be taken at approximately the same times each day. Ideally, doses should be taken at approximately 12-hour intervals, while in a fasted state. While it is realized that variations in the dosing schedule may occur, the prescribed regimen should be followed as closely as possible. Compliance with the protocol dosing schedule will be documented in the subject's chart and the electronic data capture (EDC) at each scheduled visit. Counseling regarding subject compliance may be required.

5.3.4. Dose Schedule Interruptions and Vomited Doses

Subjects who have a delay in administration of a dose of GS-9973 or GS-9973 SDD of < 6 hours should take the planned dose as soon as possible after the intended time of administration. For subjects who have a delay in administration of GS-9973 or GS-9973 SDD of ≥ 6 hours, the dose should not be taken. GS-9973 or GS-9973 SDD administration may continue but the missed dose should not be made up and the planned timing of subsequent GS-9973 or GS-9973 SDD dosing should not be altered.

Vomited doses should be retaken, but only if the tablets are visible in the vomitus.

5.3.5. Transition of GS-9973 MM formulation to GS-9973 SDD formulation

As of protocol amendment 8, subjects receiving GS-9973 MM formulation will be transitioned to the GS-9973 SDD formulation. A comparison of the GS-9973 steady-state AUC_{tau} in healthy subjects following GS-9973 MM formulation and GS-9973 SDD formulation is provided in [Figure 5-1](#) (data from studies GS-US-245-0101, GS-US-245-1222, GS-US-339-0111, GS-US-339-1627 and GS-US-339-1914), and the new dose levels for GS-9973 SDD formulation are provided in [Table 5-1](#). The GS-9973 SDD dose levels in [Table 5-1](#) are expected to provide similar GS-9973 systemic exposure as the indicated dose of GS-9973 MM formulation ([Figure 5-1](#)).

Figure 5-1. GS-9973 AUC_{tau} following GS-9973 MM and GS-9973 SDD formulations

[figure not shown]

Table 5-1. Transition of GS-9973 MM formulation to GS-9973 SDD formulation

Current dose level GS-9973 MM Dose (mg BID fasting)	Current enrollment at this dose level (N) as of March 2017	New dose level GS-9973 SDD Dose (mg BID fasting)
800	11	400
600	2	400
400	1	200
200	0	200

a All cohorts that received GS-9973 MM formulation are closed to further enrollment.

5.3.6. Management of Dose Limiting Toxicities

Adverse events and laboratory abnormalities will be graded using the CTCAE, Version 4.03. Dose modification of GS-9973/GS-9973 SDD should be performed for the following dose limiting AEs:

- Grade 4 hematological toxicities persisting for ≥ 14 days
- Grade ≥ 3 toxicities of other types

Of note, the occurrence of asymptomatic lymphocytosis will not be considered a toxicity requiring dose modification. Dose reduction will not be required for untreated vomiting, diarrhea, or constipation; interruption of dosing until these symptoms are adequately treated is permitted.

Table 5-2. GS-9973 MM Dose Levels

Dose Level	GS-9973 MM Dose (mg BID fasting)
0	800
-1	600
-2	400
-3	200

Table 5-3. GS-9973 SDD Dose Levels

Dose Level	GS-9973 SDD Dose (mg BID fasting)
CLL Prior BTK inhibitor Exposure, CLL Prior PI3K inhibitor Exposure or CLL Dose Ranging randomized to 400mg BID or Dose level 0	400
CLL Dose Ranging randomized to 200mg BID or Dose level -1	200
CLL Dose Ranging randomized to 100mg BID or Dose level -2	100

If a subject experiences an AE or laboratory abnormality that is suspected to be related to GS-9973/GS-9973 SDD, and requires a dose reduction, GS-9973/GS-9973 SDD administration should be interrupted, as necessary, until the AE or laboratory abnormality resolves or stabilizes to an acceptable degree (generally to Grade 1 or the pretreatment severity grade, whichever is higher). More frequent monitoring (eg, once per week) may be warranted until adverse events or laboratory abnormalities are clearly improving. When treatment is reinstated, the dose of GS-9973/GS-9973 SDD should be reduced by 1 dose level (see [Table 5-2](#) and [Table 5-3](#)).

Successive adjustments to progressively lower dose levels can be made. If the subject cannot tolerate GS-9973/GS-9973 SDD at the lowest dose level then the subject should discontinue GS-9973/GS-9973 SDD therapy.

After a dose is reduced, the dose need not be re-escalated, even if there is minimal or no toxicity with the reduced dose. However, if the subject tolerates a reduced dose of GS-9973/GS-9973 SDD for ≥ 4 weeks then the GS-9973/GS-9973 SDD dose may be increased to the next higher dose level, at the discretion of the investigator. Such re-escalation should strongly be considered if further evaluation reveals that the AE that led to the dose reduction was not GS-9973/GS-9973

SDD-related. Successive adjustments to progressively higher dose levels can be made at 4-week intervals up to the highest dose level. Dose escalations above the highest dose level are not allowed. Any study drug dose re-escalation must be discussed between the investigator and the Gilead Sciences Medical Monitor or designee prior to implementation.

Whenever the study drug dose is de-escalated or re-escalated, the appropriate clinic staff should dispense the study drug for the new dose level and instruct the subject/caregiver about the change in dose level.

Note: Dose modifications and clinical management for subjects who enter the study with pre-existing Grade 3 or 4 abnormalities due to their underlying malignancy will be discussed with the study Medical Monitor or designee prior to the initiation of treatment.

5.3.6.1. Guidelines for Dose Modifications

Recommendations for dose modifications based on the type and severity of adverse events or laboratory abnormalities are provided in [Table 5-4](#). The dose adjustment recommendations are based on the CTCAE grade of specific toxicities. However, exceptions are expected for subjects who initiate study treatment with low blood counts. Clinical judgment should apply, and in cases of uncertainty, the study medical monitor should be contacted.

The dose modification instructions focus on the types of events most commonly attributed to GS-9973/GS-9973 SDD or other drugs that target B-cell receptor signaling pathways. The recommendations provided in [Table 5-4](#) comprise only guidelines; variations from these recommendations may be warranted based on an investigator's individual judgment in considering potential risks, benefits, and therapeutic alternatives available to each subject.

Table 5-4. Dose Modification Guidelines

Adverse Event	Grade 1	Grade 2	Grade 3	Grade 4
Neutropenia		Maintain current dose level and schedule.		Consider G-CSF support and continue dosing at same or lower dose level at investigator discretion.
Thrombocytopenia		Maintain current dose level and schedule.		Withhold for bruising or bleeding until Grade \leq 3. May resume dosing at initial or lower dose level at investigator discretion
Dermatological	Maintain current dose level and schedule.		Withhold dosing until \leq Grade 1. Resume dosing at current dose level. If re-challenge at current dose level results in recurrence, may resume dosing at same or lower dose level at investigator discretion.	Withhold dosing until Grade \leq 1. May resume at lower dose level or discontinue dosing at investigator discretion.

Adverse Event	Grade 1	Grade 2	Grade 3	Grade 4
Gastrointestinal Inflammation-Diarrhea	Provide anti-diarrheal (e.g., loperamide) and maintain current dose level and schedule	Provide anti-diarrheal (e.g., loperamide). Withhold dosing until Grade ≤ 1 . Resume dosing at current dose level. If re-challenge results in recurrence, may resume at initial or lower dose level at investigator discretion. Consider addition of anti-inflammatory (e.g., sulfasalazine, budesonide).	Provide anti-diarrheal (e.g., loperamide). Withhold dosing until Grade ≤ 1 . Resume at lower dose level. Consider addition of anti-inflammatory (e.g., sulfasalazine, budesonide).	Provide anti-diarrheal (e.g., loperamide). Withhold dosing until Grade ≤ 1 . May resume at lower dose level or discontinue dosing at investigator discretion. Consider addition of anti-inflammatory (e.g., sulfasalazine, budesonide).
Hepatic (elevations in ALT, AST, or bilirubin)	(ALT/AST ≤ 3 xULN) (Direct Bilirubin ≤ 1.5 xULN)	(ALT/AST $>3-5$ xULN) (Direct Bilirubin $>1.5-3$ xULN)	(ALT/AST $>5-20$ xULN) (Direct Bilirubin $>3-10$ xULN)	(ALT/AST >20 xULN) (Direct Bilirubin >10 xULN)
	Maintain current dose level and schedule.	Maintain current dose level and schedule. Monitor ALT, AST, ALP, and direct bilirubin at least 1x per week.	Withhold dosing. Monitor ALT, AST, ALP, and direct bilirubin at least 1x per week until all abnormalities are Grade ≤ 1 . If direct bilirubin was Grade <3 , resume dosing at same dose level. If direct bilirubin was Grade ≥ 3 , resume at lower dose level.	Withhold dosing. Monitor ALT, AST, ALP, and direct bilirubin at least 1x per week until all abnormalities are Grade ≤ 1 . If direct bilirubin was Grade <4 , resume dosing at lower dose level. If direct bilirubin was Grade 4, discontinue dosing.
Pneumonitis (dyspnea, cough, hypoxia and/or diffuse interstitial pattern or ground-glass opacities on chest CT and no obvious infectious cause)	Maintain current dose level and schedule. Consider Pneumocystis therapy	Withhold dosing until Grade ≤ 1 . Consider systemic corticosteroids and Pneumocystis treatment. May resume at initial or lower dose level at investigator discretion.	Withhold dosing until Grade ≤ 1 . Consider systemic corticosteroids and consider Pneumocystis treatment. May resume at lower dose level or discontinue dosing at investigator discretion.	
Other Study Drug Related, Non-hematological Adverse Events	Maintain current dose level and schedule		Withhold dosing until Grade ≤ 1 . May resume dosing at initial or lower dose level or discontinue dosing at investigator discretion.	

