1.6.2. Rationale for Dose Exploration in GS-9973 Sensitive Malignancies

The GS-9973 dose of 800 mg BID was chosen to provide maximum drug exposure for subjects with malignant disease. As noted above, this dose and schedule resulted in consistent target coverage in normal subjects. However, it is possible that this dose and schedule results in drug exposure that exceeds what is required for maximum target coverage. If GS-9973 demonstrates promising anti-cancer activity in a cohort, exploration of lower doses may be required before further studies are pursued. If these 2 conditions are met, additional cohorts of 40 subjects with that malignancy may be studied to evaluate the safety profile, pharmacodynamic parameters and anti-tumor activity at lower GS-9973 doses. GS-9973 doses of 200 or 400 mg given once daily or BID will be studied in the additional cohort(s) and will be selected based upon the emerging pharmacodynamic, pharmacokinetic and anti-tumor data from the subjects already studied. Subjects who are treated at lower doses of GS-9973 should have their dose escalated up to 800 mg BID at the time of disease progression if the investigator feels it is in the subject's best interest. As of protocol amendment 8, subjects receiving GS-9973 MM formulation will be transitioned to the GS-9973 SDD formulation (Section [5.3.5](#)).

Transaminase Elevations Following Treatment with GS-9973

ALT and AST elevations have occurred in 13 of 109 subjects evaluated on this study; all subjects received GS-9973 800 mg BID. The ALT elevations were generally higher than the AST elevations, consistent with a hepatic origin. The distribution of highest ALT elevations were 1 Grade 1, 0 Grade 2, 6 Grade 3 and 5 Grade 4. GS-9973 dosing was continued for Grade 1 and 2 elevations and these subjects did not develop Grade 3 or 4 transaminase elevations. Dosing was interrupted for Grades 3 and 4 elevations. In the 4 subjects for whom GS-9973 was interrupted, in each case the ALT and AST values were lower at the next determination and returned to Grade 1 or less after 7, 12 and 21 days (Grade 3's) and after 27 days (Grade 4). Two subjects were subsequently re-started on GS-9973 at 600 mg BID without recurrence of the ALT elevation. Based upon this experience, we have provided specific guidance in the protocol for the management of Grade 3 and 4 transaminase elevations.

1.7. Rationale for Amendment 5

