1.7.1. Initial Clinical Experience with GS-9973 in Subjects with CLL

The CLL cohort for this study has completed accrual. The initial results were presented at the 2013 American Society of Hematology Annual Meeting ([Sharman 2013](#)). The results were later updated in the GS-9973 Investigator's Brochure Fourth Edition dated 14-March-2014. GS-9973 was generally well tolerated; adverse events regardless of cause that occurred in more than 10% of subjects are listed in [Table 1-1](#). Transient grade 3 or 4 transaminase elevations, which declined upon holding GS-9973, occurred in 11 of 109 (10.1%) of subjects. Four subjects were re-challenged and remain on study without recurrence of the transaminase elevation, 1 withdrew consent 1 developed a Grade 2 rash and went off study and the remaining 3 were waiting for resolution prior to re-challenge.

[figure not shown]
Table 1-1. GS-339-0102: Treatment-Emergent Non-hematologic Adverse Events Occurring in $\geq 10\%$ of Subjects, N=109*

	Grade 1	Grade 2	Grade 3	Grade 4	All Grades
Any event					106 (97.2%)
Fatigue	20 (18.3%)	22 (20.2%)	9 (8.3%)		51 (46.8%)
Nausea	26 (23.9%)	10 (9.2%)	3 (2.8%)		40 (36.7%)
Diarrhoea	33 (30.3%)	5 (4.6%)	1 (0.9%)		39 (35.8%)
Decreased appetite	16 (14.7%)	9 (8.3%)			25 (22.9%)
Headache	21 (19.3%)	3 (2.8%)	1 (0.9%)		25 (22.9%)
Constipation	14 (12.8%)	8 (7.3%)	2 (1.8%)		24 (22%)
Dizziness	21 (19.3%)	1 (0.9%)			22 (20.2%)
Pyrexia	13 (11.9%)	7 (6.4%)	2 (1.8%)		22 (20.2%)
Cough	11 (10.1%)	5 (4.6%)	1 (0.9%)		17 (15.6%)
Oedema peripheral	12 (11%)	5 (4.6%)			17 (15.6%)
Insomnia	10 (9.2%)	5 (4.6%)			15 (13.8%)
Dyspepsia	6 (5.5%)	8 (7.3%)			14 (12.8%)
Vomiting	10 (9.2%)	2 (1.8%)	1 (0.9%)		14 (12.8%)
Dyspnoea	3 (2.8%)	4 (3.7%)	6 (5.5%)		13 (11.9%)
ALT increased	1 (0.9%)		6 (5.5%)	5 (4.6%)	12 (11%)
AST increased	1 (0.9%)	1 (0.9%)	7 (6.4%)	2 (1.8%)	11 (10.1%)

* Information in table is based on IB Edition 4

GS-9973 demonstrated promising results in subjects with CLL, producing a 68% nodal partial response ([Figure 1-7](#)).

Figure 1-7. GS-339-0102: Investigator Assessed Nodal Responses in CLL (n=41)

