5.3.7. Management of Low Grade Chronic Toxicities

Since subjects will be receiving the study drugs daily, low grade chronic side effects, such as nausea, fatigue and diarrhea, while not meeting the above definition for dose limiting toxicities, may not be tolerable when experienced for long periods of time. Following discussion with the Gilead Sciences Medical Monitor, dose reduction may be permitted if low grade chronic side effects cannot be managed effectively with supportive care.

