6.6. At Disease Progression

All subjects will be followed until initiation of next treatment. If the subject was not receiving study drug at the time tumor progression was documented, or was at a dose level below the maximum and could potentially tolerate a higher dose, after discussion with the Gilead Sciences Medical Monitor, the subject may continue on study and study drug may be re-started or escalated using the algorithm defined in Section [5.3.5](#) if the investigator feels it is in the subject's best interests to do so.

If the investigator feels the subject is having progressive disease, tumor imaging as described in Section 6.12 should be carried out unless the most recent imaging had documented progressive disease. The images and any other material needed to document progression are to be transferred to the IRC as soon as possible. While waiting for confirmation of progressive disease from the IRC, the subject should continue to receive study drug unless his/her medical condition warrants immediate treatment with different therapy. When progression is confirmed, the following procedures should be carried out while the subject is still receiving study drug.

- Complete physical examination including weight
- Vital signs including blood pressure, respiratory rate, pulse, oxygen saturation by pulse oximetry, temperature
- Karnofsky performance status (see Section 6.9.3)
- Concomitant Medication Review
- Obtain blood samples for:
 - Chemistry (see Section 6.9.8)
 - Hematology (see Section 6.9.8)
 - Coagulation (see Section 6.9.8)
 - GS-9973/GS-9973 SDD plasma concentration (excluding subjects off study drug at time of progression)

For subjects with SLL, CLL or MCL

- CTC Molecular characterization (see Section 6.14)
- Cytokines and chemokines (see Section 6.13.1)
- CTC RNA pre-dose (see Section 6.13.2)

CCI

- Record the approximate number of hours between the last 2 doses of study drug and the time the blood samples for plasma concentration were obtained (excluding subjects off study drug at time of progression)
- Urine pregnancy test (females of childbearing potential)

- For CLL subjects a bone marrow biopsy/aspirate will be collected to confirm a PD. If the nature of PD does not require bone marrow confirmations, it is not necessary to obtain a bone marrow biopsy/aspirate (See Section [6.20](#)).
- Collect used/unused study drug and assess study drug compliance by pill counts (excluding subjects off study drug at time of progression)

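### Table 5-4 has no rule specific to a combined ALT/AST and direct-bilirubin rise: such a rise gets only the stricter single-marker action, and restart needs no work-up or medical-monitor agreement

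*Protocol*

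**What the plan says.** **Hepatic row, Table 5-4 (Protocol 5.3.6.1).**
- Grade 2 (ALT/AST above 3 to 5 times ULN, or direct bilirubin above 1.5 to 3 times ULN): keep the dose, with liver tests at least weekly.
- Grade 3 (ALT/AST above 5 to 20 times ULN, or direct bilirubin above 3 to 10 times ULN): hold until all abnormalities are Grade 1 or less. If direct bilirubin was below Grade 3, "resume dosing at same dose level. If direct bilirubin was Grade" 3 or higher, the restart is one level lower.
- Grade 4 (ALT/AST above 20 times ULN, or direct bilirubin above 10 times ULN): the same hold. With direct bilirubin below Grade 4, "resume dosing at lower dose level. If direct bilirubin was Grade 4, discontinue dosing".

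**General safeguards.**
- Section 5.3.6.1 calls the table guidance and asks for medical-monitor contact when the investigator is uncertain.
- Section 5.3.6 lists non-hematological toxicity of Grade 3 or higher as a reason for dose modification. For a related event that requires a reduction it says: "When treatment is reinstated, the dose of GS-9973/GS-9973 SDD should be reduced by 1 dose level".
- Section 5.6 calls for evaluation in consultation with the monitor if a subject's condition changes substantially, and for withdrawal if continuing would put the subject at risk.
- Section 7.10 has toxicities brought to the monitor's attention and clinically significant Grade 3 or 4 laboratory values repeated.

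**Where prior monitor discussion is required.**
- Section 5.3.6: "Any study drug dose re-escalation must be discussed between the investigator and the Gilead Sciences Medical Monitor or designee prior to implementation".
- Section 5.3.7: "Following discussion with the Gilead Sciences Medical Monitor, dose reduction may be permitted if low grade chronic side effects" cannot be managed with supportive care.
- Section 6.6, at progression: "after discussion with the Gilead Sciences Medical Monitor, the subject may continue on study and study drug may be re-started or escalated".

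**Clinical experience.**
- Section 1.6.2: "Two subjects were subsequently re-started on GS-9973 at 600 mg BID without recurrence of the ALT elevation". It also says that subjects dosed through Grade 1 and 2 elevations did not develop Grade 3 or 4.
- Section 1.7.1: "Four subjects were re-challenged and remain on study without recurrence of the transaminase elevation".

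**The concern.** A transaminase rise with conjugated bilirubin suggests that liver function is affected, which an isolated ALT rise does not. That is a clinical judgement, not a statement in the documents. The documents do show that the drug's known bilirubin mechanism, UGT1A1 inhibition, is offered as an explanation for total and indirect bilirubin only (Sections 1.5.3 and 5.3.8.1). A new direct-bilirubin rise alongside ALT/AST is therefore not accounted for by that mechanism. As written, such a subject can stay on drug or restart on the table alone, with no one required to look for a cause or agree to the restart.

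A second matter arises once a subject stops for liver toxicity. Section 6.5 follows subjects who stop for reasons other than progression every 6 months, or more often where local care does so. Sections 6.7, 6.20.3, 6.21.3 and Appendix 2 (footnotes c and i) keep the scheduled imaging. The choice affects whether the subject contributes to the primary landmark.

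**Working it through.** **1. Does the combination ever matter?** Grade ALT/AST 0 to 4 and direct bilirubin 0 to 4, giving 5 × 5 = 25 pairs. Assume that the worse grade selects the column, which the table does not state. Compare each pair's action with the stricter of the two actions the markers would draw alone. The pairs that differ number **0 of 25**. The nine pairs with both markers at Grade 2 or higher are:

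| ALT/AST | Direct bilirubin 2 | Direct bilirubin 3 | Direct bilirubin 4 |
|---|---|---|---|
| Grade 2 | continue, weekly tests | hold, lower dose | discontinue |
| Grade 3 | hold, same dose | hold, lower dose | discontinue |
| Grade 4 | hold, lower dose | hold, lower dose | discontinue |

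Each entry equals the stricter single-marker action. The weakest are Grade 2 with Grade 2, and Grade 3 ALT/AST with Grade 2 direct bilirubin.

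**2. Do the general safeguards fill the gap?** Sections 5.3.6, 5.3.6.1, 5.6 and 7.10 provide judgement, notice, repeat testing and consultation on a substantial change. None names the combination, and none requires a cause work-up or monitor agreement before restart.

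**3. How much experience is there?** None of these figures measures the combined pattern, because bilirubin status is not reported.
- Grade 3 or 4 transaminase elevations (Section 1.7.1): 11/109 = 10.1%, which reproduces the plan's figure. Exact 95% interval 5.1% to 17.3%.
- Re-challenge without recurrence, one-sided 95% upper limit 1 − 0.05^(1/n). For n = 4 (Section 1.7.1, dose not stated): 1 − 0.05^(1/4) = 53%. For n = 2 (Section 1.6.2, at 600 mg): 1 − 0.05^(1/2) = 78%. The two reports may overlap.
- Dosing through Grade 1 or 2: Section 1.6.2 counts 13 of 109 with any elevation and Section 1.7.1 counts 11 of 109 with Grade 3 or 4. If both describe the same subjects and data cut, 13 − 11 = 2 subjects had a worst grade of 1 or 2.

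**4. Imaging.** Scans fall at Weeks 8, 16, 24, 36 and 48 (Section 6.5). Taking 6 months as 26 weeks:
- Last scan Week 8: next at 8 + 26 = Week 34, with Weeks 16 and 24 missed.
- Last scan Week 16: next at 16 + 26 = Week 42, with Weeks 24 and 36 missed.

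Protocol 8.4.2 and SAP Appendix 2 (Table 13-1, step 4) censor a progression or death that follows two or more consecutive missing assessments, at the last adequate assessment before them. In the first case that is Week 8, before either landmark. In the second it is Week 16, before the Week 24 landmark.

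**The case against.** The strongest reply is that the row is not blind to bilirubin. Direct bilirubin decides the restart dose at Grades 3 and 4, and restart waits until every liver abnormality is Grade 1 or less. A reader might infer that a combined rise has no rule at all, but the table above shows an action for every pair. A reader might also infer that only direct bilirubin above 10 times ULN ends treatment. That is too strong as well: a subject at the lowest level has no lower dose to restart on, and Sections 5.3.6 and 5.6 end treatment when the lowest level is not tolerated. Section 5.6 gives more than an option to withdraw, since it calls for evaluation in consultation with the monitor. These points stand. They narrow the gap to the missing combination-specific trigger.

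The guidance was also written from experience, and that experience was favourable. This stands too, but it is small. Both restarts in Section 1.6.2 were one level below 800 mg, so they do not directly test a same-dose restart. Exposure did plateau from 600 mg in healthy subjects (Section 1.6.1), so they may come close to one.

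No other Table 5-4 row requires monitor agreement before restart, and the three places that require discussion concern different decisions. They show that the requirement is familiar in this protocol. They do not show that it was owed here.

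On imaging, held subjects are already covered: Sections 6.5 and 6.12 keep scans on schedule regardless of dose interruptions. Only the 6-month sentence for subjects who stop conflicts, and it yields to more frequent local care.

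**Conclusion.** The point holds as a low-cost safety improvement. Table 5-4 has no combination-specific rule (0 of 25 pairs), so a combined Grade 2 rise continues, and a Grade 3 ALT/AST rise with Grade 2 direct bilirubin restarts at the same dose, without a required work-up or monitor agreement. A reader might go further and infer that the drug has caused combined liver injury, or that restart has proved unsafe. The documents support neither. No combined case is documented, the frequency is unknown, and no recurrence on re-challenge is reported. With upper limits of 53% and 78%, recurrence is not ruled out either.

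The conclusion assumes that the worse grade selects the column and that a combined rise deserves more caution than an isolated one. The imaging conflict is real but separate. It affects any subject who stops for a reason other than progression, and it leads to early censoring only if the 6-month interval is actually used and progression or death follows.

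**What to change.** 1. **Table 5-4, hepatic row.** Add: if ALT/AST is above 3 times ULN and direct bilirubin is newly Grade 2 or higher (above 1.5 times ULN, the table's own limit), hold dosing and evaluate the cause. Restart only after recovery to Grade 1 or less and with medical-monitor agreement, normally one level lower. For subjects already at the lowest level (100 mg SDD in Table 5-3, also a randomised arm), the investigator and monitor decide between the same dose and discontinuation. A compulsory reduction would force those subjects off drug.
2. **SAP 7.2.1.2 (optional).** Add one row counting subjects who meet this criterion. Direct bilirubin is already in the chemistry panel (Protocol Table 6-1). The planned summaries go one test at a time, so co-occurrence shows only in the by-subject listings.
3. **Protocol 6.5 (separate).** Replace the 6-month interval with the 8- to 12-week imaging of Sections 6.20.3, 6.21.3 and Appendix 2 for subjects who permanently stop drug without progression.

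**Cost.** One table line, one changed sentence and, if wanted, one output row from data already collected. A probably small but unquantified number of subjects would have a delay or a reduction, which is a real loss in relapsed disease. Reductions in the dose-ranging cohort (20 planned per arm) would slightly blur its by-dose PFS estimates.
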